
16.0 ETHICAL AND REGULATORY CONSIDERATIONS

The following must be observed to comply with Food and Drug Administration regulations for the conduct and monitoring of clinical investigations; they also represent sound research practice:

Informed Consent

The principles of informed consent are described by Federal Regulatory Guidelines (Federal Register Vol. 82, No. 12, January 19, 2017) and the Office for Protection from Research Risks Reports: Protection of Human Subjects (Code of Federal Regulations 45 CFR 46). They must be followed to comply with FDA regulations for the conduct and monitoring of clinical investigations.

Institutional Review

This study must be approved by an appropriate institutional review committee as defined by Federal Regulatory Guidelines (Ref. Federal Register Vol. 82, No. 12, January 19, 2017) and the Office for Protection from Research Risks Reports: Protection of Human Subjects (Code of Federal Regulations 45 CFR 46).

Drug Accountability

An investigator is required to maintain adequate records of the disposition of investigational drugs according to procedures and requirements governing the use of investigational new drugs as described in the Code of Federal Regulations 21 CFR 312.

Monitoring

This study will be monitored by the Clinical Data Update System (CDUS) Version 3.0. Cumulative CDUS data will be submitted quarterly to CTEP by electronic means. Reports are due January 31, April 30, July 31 and October 31.

Confidentiality

Please note that the information contained in this protocol is considered confidential and should not be used or shared beyond the purposes of completing protocol requirements until or unless additional permission is obtained.

16.1 Expedited reporting for commercial agents

Commercial reporting requirements are provided in [Table 16.1](#). If there is any question about the reportability of an adverse event or if on-line CTEP-AERS cannot be used, please telephone or email the SAE Program at the Operations Office, [name] or [contact], before preparing the report.

Table 16.1. Expedited reporting requirements for adverse events experienced by patients on all study arms within 30 days of the last administration of the commercial agent.

Attribution	Grade 3		Grade 4		Grade 5 ^a	
	Unexpected	Expected	Unexpected	Expected	Unexpected	Expected
Unrelated or Unlikely	CTEP-AERS	CTEP-AERS	CTEP-AERS	CTEP-AERS	CTEP-AERS	CTEP-AERS
Possible, Probable, Definite	CTEP-AERS	CTEP-AERS	CTEP-AERS	CTEP-AERS	CTEP-AERS	CTEP-AERS
CTEP-AERS: Indicates an expedited report is to be submitted via CTEP-AERS within 15 calendar days of learning of the event ^b .						
^a This includes all deaths within 30 days of the last dose of treatment with a commercial agent(s), regardless of attribution. Any death that occurs more than 30 days after the last dose of treatment with a commercial agent(s) and is attributed (possibly, probably, or definitely) to the agent(s) and is not due to cancer recurrence must be reported according to the instructions above.						
^b Submission of the on-line CTEP-AERS report plus any necessary amendments generally completes the reporting requirements. You may, however, be asked to submit supporting clinical data to the Operations Office in order to complete the evaluation of the event. If requested, the specified data should be sent within 5 calendar days by fax to [name].						

18.1 Translational Medicine

HBV DNA, HBsAg, ultrasensitive HBsAg, anti-HBs, HBV RNA, HBV core-related antigen (HBcrAg)

Blood specimens for 444 study participants enrolled in the main clinical study will be collected at baseline and at regular intervals after registration as outlined above in [Section 9.0](#) Study Calendar and [Section 15.0](#). Sixty sites will enroll 222 chronic HBV and 222 past HBV patients, collect blood specimens at study time points, and send specimens to the SWOG Biospecimen Bank. The SWOG Biospecimen Bank will prepare and batch-ship specimens to Toronto Centre for Liver Disease Laboratories during the main clinical study for research tests (HBV DNA, HBsAg, ultrasensitive HBsAg, HBV RNA, HBcAg, anti-HBs, and HBeAg tests) to retrospectively identify patients with HBV reactivation. The results from labs at Toronto Centre for Liver Disease will be used to determine cases of HBV reactivation and matched controls.

a. Specimen Collection and Processing:

Specimens for the TM studies will be collected in red top tubes at 5 time points (+/- 4 weeks) and processed at the site as detailed in [Section 15.0](#).

See Section 18.1d for SWOG Biospecimen Banking Instructions

At the end of the study, the bank will ship specimens to The Toronto Centre for Liver Disease labs where the following HBV tests will be performed: HBV DNA, HBsAg, ultrasensitive HBsAg, HBV RNA, HBcAg, anti-HBs, and HBeAg tests. ALT, total bilirubin, and INR will be performed as part of routine monitoring in the main clinical study SWOG [S1614](#).

b. **Translational Aim 1. To determine baseline and changes in overall immune status and HBV-specific immune response in solid tumor patients with chronic or past HBV infection receiving anti-cancer therapy, and to compare the differences in these immune responses by HBV reactivation status.**

HBV-specific T cell and B cell responses are weak in patients with chronic HBV infection. However, evidence from patients receiving immunosuppressive therapy confirms that there is ongoing immune control in chronic HBV infection. Multiple agents with different immunosuppressive and/or immunomodulatory properties have been associated with HBV-reactivation. Reactivation occurs with non-specific therapy like corticosteroids, as well as with targeted treatments like B cell-depleting agents and anti-TNF therapies. Therefore, perturbation of immune composition and/or specific antiviral pathways can result in reactivation. However, HBV reactivation does not occur in all patients who receive immunomodulatory therapies. We hypothesize that the composition, phenotype and function of immune cells at baseline will predict HBV reactivation after starting anti-cancer chemotherapy.

Aim 2 will conduct a case-control study comparing immune status in patients who develop HBV reactivation during chemotherapy with a 1:1 matched set of controls who were not on anti-HBV therapy and did not develop HBV reactivation. Specimens will be collected at the time points detailed in [Section 9.0](#) Study Calendar and [Section 15.0](#). Participants who are clinically diagnosed to have HBV reactivation will have an additional blood draw for future immune studies. All blood specimens will be collected from 444 study participants then shipped overnight to SWOG Biospecimen Bank for processing and storage in a -80°C freezer. Specimens will be sent from SWOG Biospecimen Bank to Drs. [name] and [name]'s laboratory at the Toronto Centre for Liver Disease for immune

studies detailed below. [name] and her immunology collaborators will have priority access to the specimens at SWOG Biospecimen Bank at all times.

The samples are the key novel aspect of the study. Using data from Translational Aim 1, we will identify patients with reactivation defined by increasing HBV viral load with an equal number of patients not experiencing HBV reactivation after treatment. The primary analysis will be performed on longitudinal samples comparing change from baseline upon starting chemotherapy in HBV reactivation patients and those without reactivation. Patients will be matched by age (5-year strata), sex, type of anti-cancer therapy (cytotoxic, immune or targeted) and chronic vs. past HBV.

Chemotherapeutic disruption of the immunological profile maintaining HBV control (500,000 cells). To identify population-based changes in patients experiencing HBV reactivation after chemotherapy, we will use an extensive (30+) parameter CyTOF analysis to quantify CD4, CD8, γδ, MAIT, Treg, NK CD56br, NK CD56dim, memory B cells, plasma blasts, CD14, CD14/16, CD16 monocytes, CD1c, CD141, and plasmacytoid dendritic cells. Comparison between patients that do and do not experience reactivation will identify key biomarkers to stratify patient risk of reactivation and antiviral prophylaxis decisions.

Chemotherapeutic disruption of immunological functions responsible for HBV control (1 – 2 mil cells). To measure how chemotherapeutic agents alter the functional profile of leukocytes we will stimulate lymphocytes and myeloid cells with non-specific agonists such as anti-CD3, IL-12 + IL-18, and TLR agonists. To evaluate the cytokine profile we will use conventional 13 color flow cytometry panels to measure the frequency of single/multiple cytokine positive cells. We will compare samples longitudinally within patients and between patients with and without HBV reactivation. These data have the potential to identify a functional biomarker associated with HBV reactivation and an immunological pathway responsible for HBV control.

Longitudinal analysis of HBV-specific T & B cell immunity (3 – 5 mil cells). To determine whether reactivation is the result of suppression of HBV-specific immunity vs. frequency/functional alterations we will perform HBV-specific T and B cell ELISpot. We will use a pool of overlapping peptides covering the entire HBV genome.³⁷ Because of the low frequency of HBV-specific T cells, even in patients with previous HBV infection (anti-HBc+), we will use in vitro expansion to increase the rate of HBV-specific T cell detection. To investigate the HBV-specific B cell frequency, we will isolate B cells by magnetic selection and perform HBsAg-specific B cell ELISpot. B cell frequency will be compared longitudinally in patients with and without reactivation and correlated with detection of anti-HBs antibodies in the serum of patients with both chronic and resolved HBV infection. This will allow us to evaluate how the decay of anti-HBs antibodies in the serum correlates with HBV reactivation and quantify the extent to which anti-HBV antibodies are maintaining control of HBV replication in both chronic and resolved HBV infection.

Serum analysis to identify serum biomarkers predicting HBV reactivation. We will use clinical assays to quantify HBV-specific antibodies in the serum and a comprehensive CBA or luminex assay to analyze immunological cytokines/chemokines in longitudinal serum samples. Arginase will be measured by ELISA. HBV RNA, HBcrAg and ultrasensitive HBsAg will be measured in the serum by qPCR (RNA) and ELISA (HBcrAg and ultrasensitive HBsAg) in patients who do and do not experience HBV reactivation to determine if the levels of these markers that indicated active transcription of HBV DNA in the liver increase prior to clinical reactivation and could be used as biomarkers of impending reactivation.

Understanding the serum profile of key molecules associated with HBV reactivation may provide a baseline predictor of HBV control during chemotherapy.

c. **Translational Aim 2. To identify demographic and clinical predictors and correlative immunologic biomarkers of HBV reactivation after receipt of anti-cancer therapy in patients with solid tumors and chronic or past HBV infection.**

The determinants of HBV reactivation in patients with solid tumors are not known. In this aim, we will identify the demographic and clinical predictors as well as immune correlates of HBV reactivation and hepatitis flare among all 444 study patients. For Aim 2, all immune studies will be performed on stored plasma and PBMCs that would have already been prospectively collected at predetermined time points as noted in [Section 9.0](#) Study Calendar and [Section 15.0](#) above. Immune tests will include ELISA, ICC assay, IFN-gamma elispot. If any immune test listed for Aim 2 has already been performed as part of the case control study in Aim 1, it will not be repeated in this aim. In the main clinical study, SWOG sites will collect clinical information for use in Aim 2. The following tests will be considered usual care monitoring for HBV patients receiving anti-cancer therapy and will be recorded at the study follow up time points listed in [Section 9.0](#) Study Calendar: ALT, total bilirubin, and INR. The primary outcome for Aim 2 is time to first evidence of HBV reactivation.

Statistical Analyses plan

Only the patients randomized to the standard arm of each randomized study (chronic vs. past HBV infection) will be the potential participants for this aim. A case-control analysis, using a ratio of cases to controls of 1:1, will be conducted to explore baseline and changes of overall immune status and HBV-specific immune response factors that differ between patients with vs. without HBV reactivation. Based on expected rates of HBV reactivation for patients with chronic and past HBV infection (20%), we estimate that 22 patients with chronic and 22 patients with past HBV infection (n=44 total cases) will develop HBV reactivation. Under this scenario, we will also examine a matched set of 44 control patients. Matching will occur based on age and randomized study type (chronic vs. past HBV infection). Power is low in this setting and therefore this aim is considered exploratory, with any positive findings requiring validation in future studies. For a given binary predictor (i.e. immune status, group 1 = high vs. group 2 = low), 88 total patients (44 cases and 44 controls) is sufficient to detect an absolute difference of 26% in HBV reactivation rates (i.e. 7% for group 1 and 33% for group 2), assuming the overall rate of HBV reactivation is 20%, using a 2-arm binomial alpha=.05 test with 80% power. In addition, changes in overall immune status and HBV-specific immune responses after onset of cytotoxic chemotherapy or immunotherapy will be described for the cases and controls using descriptive statistics (means, standard deviations). To avoid incorrect inference induced by the potentially endogenous relationship between HBV reactivation and immune response, landmark analyses will be used, conditioning on patients surviving to a given assessment time without developing HBV reactivation.

The study will also assess the association of potential risk factors (including demographic, clinical, and immunologic markers) for HBV reactivation. For any potential demographic, clinical, or immunologic factor, time-to-HBV reactivation will be examined using Cox regression, adjusting for the stratification factors specified in the main clinical study. Analyses will be conducted for each randomized study (chronic vs. past HBV), each with a total sample size of n=222 patients. For instance, to identify a hazard ratio of 2.5 between patients with or without a given condition (say, status for a specified candidate marker or

composite, yes vs. no), 222 patients will give 87% power using alpha=.05 two sided tests with 80% survival at 1 year of follow-up data. Power will vary as a function of the proportion in subgroups (i.e. 40% have risk factor vs. 60% do not) and the hazard ratio as indicated in [Table 18.1](#) below, and it will generally be adequate to identify hazard ratios of ≥ 2.5 .

Table 18.1. Power to detect a specified difference in risk of HBV reactivation or hepatitis flare

Power	% of Patients with vs. without a Risk Factor			
Hazard Ratio	50 vs. 50	40 vs. 60	30 vs. 70	20 vs. 80
2.0	77%	73%	66%	54%
2.5	90%	87%	81%	68%
3.0	95%	93%	88%	76%
3.5	97%	96%	91%	81%

TM Endpoints

Hepatitis B-associated hepatitis defined as ALT $>3\times$ ULN and one of the following: ≥ 2 log (100-fold) increase in HBV DNA compared to baseline in patients with detectable HBV DNA at baseline, or HBV DNA ≥ 3 log (1,000) IU/mL in a patient with previously undetectable HBV DNA, or HBV DNA ≥ 4 log (10,000) IU/mL if baseline HBV DNA not available, or HBsAg seroreversion (HBsAg- to HBsAg+) in a patient previously HBsAg-.

Hepatitis B reactivation defined as one of the following: ≥ 2 log (100-fold) increase in HBV DNA compared to baseline in patients with detectable HBV DNA at baseline, or HBV DNA ≥ 3 log (1,000) IU/mL in a patient with previously undetectable HBV DNA, or HBV DNA ≥ 4 log (10,000) IU/mL if baseline HBV DNA not available, or HBsAg seroreversion (HBsAg- to HBsAg+) in a patient previously HBsAg-.

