11.2 Secondary Endpoints

The main secondary objective for each randomized cohort is to determine the incidence of HBV reactivation among patients with solid malignancies and chronic or past HBV infection during or after completion of anti-cancer therapy. Based on preliminary data, it is anticipated that 20% of patients will experience HBV reactivation on the standard arm of each of the randomized trials. Estimates of HBV reactivation at one year will be derived using cumulative incidence to account for competing risks. Under this scenario, a sample size of n=222 patients for each randomized study will allow the investigators to estimate the confidence interval to within $\pm 6\%$ (based on the upper bound of the 95% confidence

interval using an exact binomial in patients with complete follow-up), if the assumed incidence is at least 20%. Thus, this sample size will allow the confidence interval to be estimated to within $\pm 31.1\%$ of the assumed incidence (the “relative accuracy”, defined as: (95% CI upper bound – p)/p], where p is the assumed incidence). This estimate is conservative as it is based on the assumption of no information from the 10% of patients estimated to drop out.

The investigators will also compare HBV reactivation rates by arm within each randomized trial. Based on a two-sample survival design accounting for the competing risk of death (~20% deaths at 1 year [hazard rate of 0.223]), and a one-sided alpha=0.05 test, then n=222 patients (111 per arm) will give 81% power to detect a hazard ratio for HBV reactivation for experimental to standard arms of 0.47, representing a 53% reduction in the hazard risk of HBV reactivation in the first year (from a hazard=0.223 down to hazard=0.105), or an absolute reduction of 50% (from 20% down to 10%). Multivariable Cox regression will compare the effect of intervention assignment, adjusting for the stratification factors specified in the main clinical study.

The investigators will also determine the cumulative incidence of the combined endpoint of adverse liver events plus HBV reactivation, as well as the cumulative incidence of hepatitis flare, by arm within each randomized trial and compare it between the arms in similar fashion.

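### Controls for the exploratory immune case-control study need not be in follow-up when their matched case reactivates, and the landmark rule only partly covers this

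*Combined protocol and SAP*

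**What the plan says.** Section 18.1 (Translational Aim 1) describes a case-control comparison of immune status. Cases are patients who reactivate; each is paired with a "1:1 matched set of controls who were not on anti-HBV therapy and did not develop HBV reactivation". The same subsection gives the matching factors: "Patients will be matched by age (5-year strata), sex, type of anti-cancer therapy (cytotoxic, immune or targeted) and chronic vs. past HBV".

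The Statistical Analyses plan within Section 18.1 restricts the source population ("Only the patients randomized to the standard arm of each randomized study") and gives a shorter list: "Matching will occur based on age and randomized study type (chronic vs. past HBV infection". It expects 22 cases per cohort, 44 in all, with 44 controls. It also states that "landmark analyses will be used, conditioning on patients surviving to a given assessment time without developing HBV reactivation", and it describes the aim as exploratory and low in power.

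Sample timing is in Section 15. Serum is drawn every 8 weeks and at reactivation (15.1). Optional whole blood for the cell assays is drawn at registration, at weeks 8–12, at week 24 and at reactivation (15.2). Follow-up runs to death or 24 months (7.8).

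**The concern.** Never having reactivated is a status known only at the end of follow-up. A patient who dies at month 2 satisfies it although later reactivation could not have been seen. A patient who is reactivation-free on the case's date but reactivates afterwards does not satisfy it. Follow-up time appears in neither matching list, so nothing in the selection rule makes the control's observation period cover the case's.

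Two comparisons are exposed. The stated hypothesis is that immune composition, phenotype and function at baseline predict reactivation. At baseline every patient is alive and event-free, so early deaths and dropouts enter as non-reactivators. The serum work asks whether markers rise ahead of clinical reactivation, which requires a control observed over the same period as the case.

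**Working it through.** **Inputs from the documents**
- Patients per standard arm: 111 (Section 11.2: "n=222 patients (111 per arm) will give 81% power").
- Reactivation on the standard arm: "it is anticipated that 20% of patients will experience HBV reactivation on the standard arm of each of the randomized trials". The accompanying hazards run "from a hazard=0.223 down to hazard=0.105", so r = 0.223 per year.
- Competing death: d = 0.223 per year, about 20% at one year (11.1).
- Non-death dropout: about 10%, with no time base (11.1).
- Follow-up: 24 months (7.8).

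**Assumptions**
- Exponential times. The plan states this for liver events and death; it is extended here to reactivation and dropout.
- Dropout hazard c = 0 (none), −ln(0.9)/2 = 0.0527 (10% over two years) or −ln(0.9) = 0.1054 (10% per year).
- Controls are drawn at random from never-reactivators.

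**The plan's own figures.** Cases: 0.20 × 111 = 22.2 per cohort, hence 44. Size for 7% versus 33%, two-sided 0.05, 80% power:
- Uncorrected: n = [1.96·√(2·0.2·0.8) + 0.842·√(0.07·0.93 + 0.33·0.67)]² / 0.26² = 36 per group.
- With continuity correction: (36/4)·[1 + √(1 + 4/(36·0.26))]² = 43.4, so 44 per group.

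The 88 patients reproduce and are not in dispute.

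**Share of pairs affected.** Let L = r + d + c, q = (d + c)/L, and τ = the case window.
- Case times have density proportional to exp(−Lt) on (0, τ).
- Never-reactivators at τ consist of early exits, A = q(1 − exp(−Lτ)), and patients who complete, B = exp(−Lτ).
- A random never-reactivator has exited by time t with probability q(1 − exp(−Lt))/(A + B). Averaging over case times replaces 1 − exp(−Lt) by half of 1 − exp(−Lτ).
- So P(control exits before the case reactivates) = ½·A/(A + B).
- Expected cases per arm = 111·(r/L)·(1 − exp(−Lτ)).

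| Window τ | Dropout | A | B | Pairs affected | Cases per arm |
|---|---|---|---|---|---|
| 1 year | none | 0.180 | 0.640 | 11.0% | 20.0 |
| 1 year | 10% over 2 years | 0.217 | 0.607 | 13.2% | 19.5 |
| 1 year | 10% per year | 0.252 | 0.576 | 15.2% | 19.0 |
| 2 years | none | 0.295 | 0.410 | 20.9% | 32.8 |
| 2 years | 10% over 2 years | 0.349 | 0.369 | 24.3% | 31.3 |
| 2 years | 10% per year | 0.398 | 0.332 | 27.3% | 30.0 |

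The one-year rows give 19–20 cases per arm, close to the planned 22. The two-year rows give 30–33. On 44 pairs, 11.0–15.2% is 44 × 0.110 = 4.8 to 44 × 0.152 = 6.7, so about 5 to 7 pairs.

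**Pool left under risk-set sampling.** Patients alive, followed and reactivation-free per standard arm are 111·B: 64–71 at one year and 37–45 at month 24, before matching on covariates.

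**The case against.** The strongest reply is that the plan is not blind to follow-up. Under the landmark rule, a control who died before an assessment time does not enter that comparison. The Statistical Analyses plan also examines time to reactivation by Cox regression on 222 patients per cohort, where early exits would be censored and not counted as non-reactivators. A reader might infer from the control definition that no follow-up condition exists anywhere; these two provisions show otherwise. They do not settle control selection, however. Landmark times are not given, the baseline landmark excludes nobody, and a control lost at a later landmark leaves its case unmatched. The immune tests listed for the full-cohort work are ELISA, intracellular cytokine staining and ELISpot; the CyTOF panel is described only for the case-control comparison.

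A second reply concerns size. A reader might infer that about a quarter of pairs are affected. That needs reactivations to accrue over 24 months at 0.223 per year, which yields 30–33 cases per arm against the plan's 22. The longer window is not ruled out, since follow-up lasts 24 months, but it is not the one that the case count fits. Random pairing may also be pessimistic: controls are picked at the end of the study, and a change-from-baseline analysis needs a post-baseline sample. If controls had to reach week 8, the shares fall to 8–11% (one year) or 17–23% (24 months); if week 24, to 3–4% or 11–15%. The plan states neither requirement.

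Third, the result is a count of pairs, not a bias. Nothing in the documents shows that patients who leave early differ in immune status, or in which direction. Comparing patients who do and do not reactivate is also a recognised contrast, so barring later reactivators is partly a matter of design preference. These points stand.

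**Conclusion.** The point holds as a minor, inexpensive improvement to an exploratory aim; no trial conclusion depends on it. Control selection in Section 18.1 states no requirement that the control be in follow-up when the case reactivates, and the landmark rule covers only later assessment times.

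The size is about 11–15% of pairs on the one-year window that fits the planned 44 cases, or 21–27% on a 24-month window. Both ranges rest on exponential times, random pairing and an assumed dropout time base.

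A reader might go on to infer that the baseline immune comparison is biased. The documents do not support that: they give no basis for the direction or size of any bias. Nor do all longitudinal samples suffer. A control who leaves after week 24 has already reached every scheduled whole-blood draw, so the longitudinal exposure after that week concerns the 8-weekly serum series.

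**What to change.** In Section 18.1, replace the never-reactivated definition with risk-set sampling. For each case, draw the control from patients in the same matching cell who are alive, in follow-up, reactivation-free and off antivirals at the case's reactivation time. Analyse the pairs by conditional logistic regression. Use one matching list in both the Translational Aim 1 text and the Statistical Analyses plan, since the former includes sex and therapy type and the latter does not.

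By construction, no control will then have left before its case reactivates. The gain lies in the baseline comparison and the serum series. The change cannot provide control cell samples after week 24, because later whole-blood draws are taken only at reactivation. It needs a short text edit and no new visits or specimens, as banked samples are released at the end of the study. The cost is thinner matching cells for late cases: 37–45 patients per standard arm remain at risk at month 24 before covariate matching, and fewer will have given the optional whole blood.

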6.0 STRATIFICATION FACTORS

6.1 Cohort 1: Chronic HBV cohort

Patients with chronic HBV will be randomized between Arm 1 (prophylactic anti-HBV therapy) or Arm 2 (upon indication anti-HBV therapy) using a dynamic allocation scheme. Patient randomization to the two treatment arms will be balanced on:

- Planned cancer therapy type: cytotoxic (with or without immunotherapy or targeted therapy) vs. immunotherapy alone vs. targeted therapy alone vs. immunotherapy and targeted therapy.

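### The Aim 2 Cox models for HBV reactivation are stated for both arms without a term for randomized arm, so any factor measured after Arm 1 starts its antiviral can be confounded by arm

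*Combined protocol and SAP*

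**What the plan says.** The statistical plan under Translational Aim 2 in Section 18.1 has two parts. The first is a 1:1 case-control comparison, introduced by a restriction: "Only the patients randomized to the standard arm of each randomized study" can take part in this aim. The second covers any demographic, clinical or immunologic factor: "time-to-HBV reactivation will be examined using Cox regression, adjusting for the stratification factors specified in the main clinical study". On its size the plan says: "Analyses will be conducted for each randomized study (chronic vs. past HBV), each with a total sample size of n=222 patients". The Aim 2 introduction speaks of predictors and "immune correlates of HBV reactivation and hepatitis flare among all 444 study patients", and Section 2.1 also gives 444.

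Section 6.1 lists one stratification factor for Cohort 1: "Planned cancer therapy type: cytotoxic (with or without immunotherapy or targeted therapy) vs. immunotherapy alone vs. targeted therapy alone vs. immunotherapy and targeted therapy". Section 6.2 adds one antibody-status factor for Cohort 2. Arm is not a stratification factor. Section 11.2, which compares reactivation between arms, names intervention assignment as a model term and mentions the stratification factors separately. The adjustment phrase therefore does not include arm.

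**The concern.** In Cohort 1, Arm 1 starts an antiviral as soon as possible after registration (Section 7.2a). Section 2.1 says such drugs can prevent reactivation, and Section 11.2 states that the sample size "will give 81% power to detect a hazard ratio for HBV reactivation for experimental to standard arms of 0.47". If the drug also shifts a candidate marker, arm is a common cause of marker and outcome. A pooled model without arm then credits the marker with part of the drug's effect.

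The factors are not restricted to pre-treatment values. Aim 2 uses stored samples from the scheduled visits, and Section 15.1 allows the registration serum to be drawn up to 4 weeks either side of registration, when an Arm 1 patient may already be on drug. At stake is Translational Objective 1.3b: a marker that mainly signals being on an antiviral could be reported as a predictor of reactivation. Arm 3 starts protocol treatment only after reactivation (Section 7.3a), so the mechanism concerns mainly Cohort 1.

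**Working it through.** **1. Which population does the plan's power assume?** The stated figure is 87% for a hazard ratio of 2.5, a 40%/60% split and n=222 (Section 18.1). I assume a hazard of 0.223 per year in the risk-factor group (20% at one year), 0.223/2.5 = 0.089 in the other group, and 24 months of follow-up (Section 7.8).

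- Freedman-type formula, two-sided 0.05, no competing death. Events: 88.8 × (1 − 0.8²) + 133.2 × (1 − exp(−0.1785)) = 32.0 + 21.8 = 53.7. Then √(53.7 × 4 × 0.4 × 0.6) × (1.5/3.5) − 1.96 = 1.12, so power is 86.8%.
- Schoenfeld formula, 222 less 10% dropout = 200, two-sided, no competing death. Events: 48.4. Then √(48.4 × 0.24) × ln 2.5 − 1.96 = 1.16, so power is 87.8%.
- Freedman-type formula, n=222, death hazard 0.223, one-sided 0.05: 43.9 events, 87.2%. This setting matches 15 of the 16 cells of Table 18.1 within 2 points, although the text says two-sided.

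The same three settings at half the size give 58.6%, 59.8% and 62.6%. Across all the formulas tried with n=111 and 24 months, the range is 50% to 75%. The stated power presupposes both arms. Section 11.2 confirms the split: "n=222 patients (111 per arm) will give 81% power to detect a hazard ratio for HBV reactivation".

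**2. Events by arm.** With hazards of 0.223 and 0.105 for reactivation and 0.223 for death (Section 11.2), over 24 months:

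- Arm 2: 111 × (0.223/0.446) × (1 − exp(−0.892)) ≈ 33.
- Arm 1: 111 × (0.105/0.328) × (1 − exp(−0.656)) ≈ 17.

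The total is about 50.

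**3. Size of the bias for a null marker.** Let p1 and p2 be the shares with a high marker in Arms 1 and 2, and θ = 0.47. With equal arms, the average-hazard approximation is

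HR ≈ [(p2 + θp1)/(p2 + p1)] ÷ [((1 − p2) + θ(1 − p1))/((1 − p2) + (1 − p1))].

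For p1 = 0.3 and p2 = 0.5: (0.641/0.8) ÷ (0.829/1.2) = 0.801/0.691 = 1.16. For 0.2 and 0.6 it gives 1.34, and for 0.1 and 0.7 it gives 1.55.

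Two simulations agree. One used n=200 with 4,000 trials per scenario, the other n=222 with 1,500 trials per setting. Both had a death hazard of 0.223, 24 months and two-sided 0.05.

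| Gap between arms | n=200: shares high, Arm 2 / Arm 1 | HR, false positives | n=222: shares high, Arm 2 / Arm 1 | HR, false positives |
|---|---|---|---|---|
| 20 points | 50% / 30% | 1.2, 8% | 60% / 40% | 1.18, 8% |
| 40 points | 60% / 20% | 1.35, 18% | 70% / 30% | 1.34, 18% |
| 60 points | 70% / 10% | 1.6, 34% | 80% / 20% | 1.57, 34% |

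Stratifying by arm (n=200) gives 5% throughout. An arm term (n=222) gives hazard ratios of 1.00 to 1.02 and 4.5% to 5.4%.

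**4. Where there is no bias.** A null marker balanced across arms (50%/50%) gives a hazard ratio of 1.00 and 4.7% without an arm term. A true baseline hazard ratio of 2.5 is estimated as 2.43 without arm and 2.50 with it. If arm has no effect on reactivation, the null marker shows no bias at any prevalence gap.

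**The case against.** The strongest reply is the standard-arm sentence. If it governs the Cox models, Arm 1 is excluded and this confounding cannot arise. But it introduces the case-control analysis, whose 22 cases per cohort are 20% of 111. The Cox models come afterwards with their own n=222, a power that needs 222, and an aim covering all 444 patients. The sentence does not settle the matter, but it does leave the population unreconciled.

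Second, the use of post-baseline markers is an inference. Section 18.1 illustrates the Cox model with a fixed yes/no factor and mentions no time-dependent covariate. A reader might infer from "could be used as biomarkers of impending reactivation", said of HBV RNA, HBcrAg and ultrasensitive HBsAg, that those on-treatment markers enter the Cox models and will appear to predict reactivation. The documents do not support that. The sentence belongs to Aim 1, whose controls must not be on anti-HBV therapy, and no text assigns post-baseline values of these markers to the Cox models. What remains is that nothing restricts the factors to pre-treatment values.

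Third, a marker on the path from drug to reactivation is not simply spurious when unadjusted. The figures above are for a null marker only. Fourth, this is translational work, and the case-control paragraph calls its aim exploratory and asks for validation. That lowers the stakes. It does not protect a later study that also ignores arm. The landmark analyses described there condition on being free of reactivation and do not remove confounding by arm.

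**Conclusion.** The point holds in a limited form. As written, the Cox models include both arms and leave arm out. For demographic and true pre-treatment factors the consequence is negligible. For a factor measured after Arm 1 starts its antiviral, the consequence is a possible bias whose size depends on how far the drug separates the arms. The range of 1.2 to 1.6 for the hazard ratio and 8% to 34% for false positives rests on the plan's arm hazard ratio of 0.47, a marker with no effect of its own, and assumed prevalence gaps of 20 to 60 points. It would be too strong to say that prophylaxis-sensitive markers will be reported as predictors: the measurement times are unstated and the prevalences unknown. Separately, the standard-arm sentence conflicts with n=222 and with all 444 patients if it is meant to cover the Cox models.

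**What to change.** In Section 18.1, specify *Cox regression stratified by randomized arm and adjusted for the stratification factors*. For Cohort 1, add the marker hazard ratio within Arm 2 as a descriptive sensitivity analysis. It rests on about 33 events rather than 50, so it will be less precise. Any marker-by-arm interaction should be descriptive only, with about 17 Arm 1 events expected.

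Reconcile the standard-arm sentence with n=222 and the 444 patients by saying which analyses it covers. If the Cox models are meant for the standard arm only, restate the sample size as 111 per cohort and recompute Table 18.1. The 87% cell would fall to roughly 59% to 63% under the settings that reproduce it. Stating the measurement time of each factor would also show which ones are pre-treatment.

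The cost is one stratum in a model already planned and a few sentences of text. No new data are needed.
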